2.2. Study Rationale

2.2.1. Rationale for Assessment of Encorafenib in the Study Population

Tumor regression has been shown with encorafenib and binimatinib monotherapy in a *BRAF*-mutant human NSCLC xenograft model, and enhanced tumor regression was observed with encorafenib plus binimatinib combination. In human xenograft melanoma mice model, encorafenib plus binimatinib combination treatment has delayed the emergence of resistance due to RAS/RAF/MEK/ERK pathway reactivation.

The safety and tolerability of encorafenib as single agent or in combination with binimatinib is well-established in studies outside China. The overall safety profile of encorafenib is consistent with the respective mechanism of action and the known profile of *BRAF* inhibitors. The differentiated efficacy and safety profile of encorafenib is attributable to its substantially longer $T_{1/2diss}$ (see Section 2.1.4).

No targeted therapy for the treatment of *BRAF* V600E mutant NSCLC has been approved in China and vemurafenib is the only molecular-targeted drug approved for the treatment of patients with *BRAF* V600E mutant melanoma. Chemotherapy and immunotherapy (same as that for melanoma and NSCLC without oncogenic driver mutations) remain the standard treatment in China, depending on the accessibility and affordability of these drugs. There is therefore an urgent medical need for targeted therapy for Chinese melanoma and NSCLC patients with *BRAF* V600E mutation in the era of personalized healthcare.

Limited clinical data of encorafenib monotherapy (or in combination with binimatinib) is available specifically in Chinese *BRAF* V600E mutant patients. This study therefore aims to provide additional clinical safety and tolerability data with encorafenib 300 mg QD monotherapy in Chinese patients with *BRAF* V600E mutant melanoma or NSCLC to support further clinical development in combination with binimatinib.

2.2.2. Rationale for Dose

The QD dosing regimen of encorafenib is based on the available PK data and its $T_{1/2diss}$. Encorafenib 300 mg QD has been determined to be the single agent RP2D in the clinical program.

In population PK analysis, ethnicity and/or race did not appear to have any major impact on the PK of encorafenib in Asian patients compared to non-Asian patients, with no resulting major differences in the safety and efficacy profiles between the two populations. Due to the limited number of patients, these findings should be interpreted with caution.

2.3. Benefit/Risk Assessment

The observed toxicities of encorafenib are generally of low grade, monitorable and manageable by treatment modification, interruption and discontinuation in conjunction with appropriate medical management. Detailed information regarding clinical safety and the known and expected benefits and risks, including reasonably expected adverse events, is provided in the Investigator's Brochure for encorafenib. Guidance on monitoring and dose modifications is provided in Section 6.6.

2.3.1. Benefit Assessment

In real-world setting and clinical studies, the implication of *BRAF* V600E mutation remains unclear, with some data reporting unfavorable clinical outcome with chemotherapy and immunotherapy in Chinese *BRAF* V600 mutant melanoma and NSCLC population compared to *BRAF* wild-type patients (see Section 2.1.3).

Targeted therapy has not been approved for the treatment of *BRAF* V600E mutant NSCLC patients in China and vemurafenib is the only molecular-targeted drug approved for the treatment of *BRAF* V600E mutant melanoma. Given the implication of *BRAF* V600E mutation in melanoma and NSCLC, the prognosis remains unclear with some data reporting unfavorable clinical outcome with chemotherapy and immunotherapy; there is therefore an urgent medical need for efficacious and well-tolerated targeted therapies for *BRAF* V600 mutant melanoma and NSCLC patients in the era of personalized healthcare.

BRAF inhibitor monotherapy has demonstrated an acceptable safety profile along with a clinical activity in different indications. The differentiated efficacy and safety profile of encorafenib compared to other *BRAF* inhibitors (see Section 2.1.4) is due to the longer $T_{1/2\text{-diss}}$. The observed toxicities are generally of low grade, monitorable and manageable through appropriate medical intervention.

Ethnic sensitivity analyses have shown that there are no significant effect of ethnicity or race on the PK of encorafenib administered as single agent or in combination with binimetinib.

Outcomes from Study CMEK162B2301, COLUMBUS, demonstrated an overall survival benefit with both the combination therapy of encorafenib and binimetinib as well as with encorafenib monotherapy alone. However, it should be noted that in this study, while this was not the primary endpoint, the benefit was numerically (but not statistically) superior with the combination therapy compared to encorafenib monotherapy, suggesting that encorafenib is contributing significantly to the overall efficacy of the combination therapy of encorafenib and binimetinib [Dummer 2018b].

There is therefore the potential for the encorafenib treatment to be efficacious in Chinese patients with *BRAF* V600E mutant melanoma and NSCLC.

2.3.2. Risk Assessment

The safety and tolerability of encorafenib monotherapy is consistent with the respective mechanism of action and known safety profiles of *BRAF* inhibitors. The majority of the reported adverse drug reactions reflect the common adverse events observed in the clinical program and are well-characterized. Important risks associated with the administration of encorafenib are summarized in Table 2.

Table 2: Important Risks of Encorafenib and the Respective Mitigation Strategy

Important Risks	Summary of Data/Rationale for Risk	Mitigation measures
Secondary skin neoplasms: cutaneous squamous cell carcinoma and new primary melanoma	Associations have been reported with older age (≥ 65 years) for vemurafenib and dabrafenib-treated patients, and with prior skin cancer, and chronic sun exposure for vemurafenib-treated patients.	Skin neoplasms are described in the Investigator's Brochure for encorafenib. Dermatological evaluations will be performed by the investigator to monitor for the possible development of keratoacanthoma and/or squamous cell carcinoma and new primary melanoma, as these have been reported to occur with selective BRAF inhibitor treatment. Dermatological screening for skin malignancies will be performed on a regular basis. Early reporting of skin symptoms through careful and ongoing dermatologic monitoring will be performed throughout treatment.
QT prolongation	Risk factors for Torsade de Pointes other than QTc interval >500 ms or >60 ms increase from baseline value include uncorrected hypokalemia, hypomagnesemia and hypocalcemia, long QT syndrome, concomitant therapy with multiple QTc interval-prolonging drugs. Other risk factors for Torsade de Pointes include acute myocardial infarction, heart failure with reduced ejection fraction, diuretic therapy, age ≥ 65 years, female sex, family history of sudden cardiac death at <50 years, cardiac disease and history of arrhythmia or bradycardia.	Risk for QT prolongation is described in the Investigator's Brochure for encorafenib. Administration with medicinal products with a known potential to prolong QT/QTc should be avoided, where possible. Participants at high risk of QT prolongation are excluded from the study. Monitoring and dose adjustments for QT prolongation are outlined in Appendix 10.4.
Non-cutaneous malignancies with RAS mutation	As for other BRAF inhibitors and based on its mechanism of action, encorafenib may promote malignancies associated with RAS mutation associated with activation of RAS	Routine cancer detection and treatment as well as preventive measures for different known risk

Important Risks	Summary of Data/Rationale for Risk	Mitigation measures
	
through mutation or other mechanisms. No cases of non-cutaneous malignancy with RAS mutation possibly related to encorafenib were identified from the pooled safety data of the clinical development program, however due to the seriousness of this class-effect risk, non-cutaneous carcinoma is considered an important potential risk.
	
factors of different cancers will be performed.
 
Dose modifications are outlined in Appendix 10.4.

Over-exposure due to concomitant use with strong and moderate CYP450 3A4 inhibitors	
Encorafenib is primarily metabolised by CYP3A4. Based on the PK data, the use of strong CYP3A4 inhibitors was not allowed during clinical studies. Concomitant administration of encorafenib and strong or moderate CYP3A4 inhibitors may lead to increased encorafenib exposure and potential increase in toxicity.
	
Drug-drug interactions properties of encorafenib are described in the Investigator's Brochure for encorafenib.
 
The use of strong inhibitors of CYP3A4 is prohibited.
 
Concomitant use of moderate CYP3A4 inhibitors should be avoided. If use of moderate CYP3A4 inhibitors is unavoidable and no alternatives are available, short-term use (≤ 30 days) following discussion with the sponsor may be permitted with accompanying dose reduction to one-half of the encorafenib dose before use of moderate CYP3A4 inhibitors (or as close as can be achieved without exceeding the target dose).

Over-exposure in patients with moderate to severe hepatic impairment	
Results from a dedicated clinical study indicate a 25% higher total encorafenib exposures in participants with mild hepatic impairment (Child-Pugh Class A) compared with participants with normal liver function. This translates into a 55% increase of the unbound encorafenib exposure.
 
The PK of encorafenib has not been evaluated clinically in participants with moderate (Child-Pugh Class B) or severe (Child-Pugh Class C) hepatic impairment. As encorafenib is primarily metabolised and eliminated via the liver and based on PBPK modelling, participants with moderate to severe hepatic impairment may have greater increases in exposure than participants with mild hepatic impairment. No dosing recommendation can be made in moderate or severe hepatic impairment.
	
Over-exposure in participants with moderate to severe hepatic impairment is described in the Investigator's Brochure for encorafenib.
 
Participants with impaired hepatic function, defined as Child-Pugh Class B or C should not be included the study.

Abbreviations: BRAF = B-raf murine sarcoma viral oncogene homolog B1; CYP450 = cytochrome P450; PBPK = physiologically based pharmacokinetic; PK = pharmacokinetics; RAS = rat sarcoma viral oncogene homologue.

Due to the substantially longer $T_{1/2\text{diss}}$ of encorafenib and consequently attenuated off-target effects, encorafenib has the potential to decrease BRAF inhibitor-related toxicities. Encorafenib has a differentiated safety profile compared to other BRAF inhibitors, which is mainly reflected in the lower incidence of pyrexia (dabrafenib-associated toxicity) and phototoxicity (vemurafenib-related toxicity). The majority of the observed toxicities with encorafenib are generally reversible and manageable by appropriate supportive medical care and/or dose modifications or discontinuation, and the risks will be mitigated through the implementation of the measures in Table 2 for clinical monitoring of participants during treatment.

Ethnic factors do not appear to influence the safety profile of encorafenib. These findings will be confirmed in Chinese melanoma and NSCLC participants with a *BRAF* V600E mutation in this study prior to conducting further, larger studies of encorafenib in combination with binimetinib in the Chinese population.

Review of the available safety data from post-marketing experience and clinical studies have not changed the benefit-risk profile of encorafenib which remains favorable when used in its approved indications and in accordance with the prescribing information. A review of individual case safety reports originating from Asian participants has shown that the pattern of adverse events related to study intervention grouped by Medical Dictionary for Regulatory Activities (MedDRA) is generally consistent with the global population.

2.3.3. Overall Benefit/Risk Conclusion

Taking into account the anticipated benefit and mitigating measures for the risks associated with encorafenib, the benefit of encorafenib treatment outweighs the potential risks for participants with *BRAF* V600E mutant melanoma and NSCLC in this study. The overall benefit/risk ratio is therefore deemed favorable.

3. Objectives and Endpoints

Objectives and endpoints are correlated in Table 3.

Table 3: Objectives and Endpoints in W00090GE102

Objectives	Endpoints
Primary	

 To assess the safety of encorafenib 300 mg QD in monotherapy during Cycle 1. 	
 Incidence of DLTs experienced during Cycle 1 (Days 1 to 28)
Secondary	

 To characterize the safety and tolerability of encorafenib 300 mg QD in monotherapy in Chinese participants. To provide PK data of encorafenib and its metabolite (LHY746) in monotherapy. 	
 Incidence, nature and severity of TEAEs graded as per NCI CTCAE Version 4.03, TEAEs leading to dose interruption, reduction and discontinuation, treatment-emergent SAEs and deaths Changes in clinical laboratory parameters, vital signs, ECGs Incidence of targeted TEAEs of special interest PK parameters of encorafenib and its metabolite (LHY746) after single and repeated administration

Abbreviations: DLT = dose limiting toxicity; ECG = electrocardiogram; NCI CTCAE = National Cancer Institute Common Terminology Criteria for Adverse Events; PK = pharmacokinetic; QD = once daily; SAE = serious adverse event; TEAE = treatment emergent adverse event.

4. Study Design

4.1. Overall Design

[figure not shown]
4.1.1. Study Design Overview

This is a phase 1, multicenter, open-label, single-arm study to investigate the safety and tolerability of encorafenib monotherapy in adult Chinese participants with *BRAF* V600E mutant advanced solid tumors (unresectable metastatic melanoma or metastatic NSCLC) who are *BRAF*- and *MEK*-inhibitor treatment-naïve and have failed the previous therapy(ies) for advanced metastatic disease or are not eligible to standard therapy. Participants will be eligible for the study based on identification of a *BRAF* V600E mutation in tumor tissue by a local National Medical Products Administration (NMPA) approved assay obtained prior to screening.

All participants will receive a fixed flat oral dose of 300 mg encorafenib QD.

It is planned to enrol up to six evaluable participants using a 3+3 design, shown in Figure 1.

Figure 1: Schema of 3+3 Design

Abbreviations: DLT = dose limiting toxicity; TSC = Trial Steering Committee

- Three participants will initially be enrolled and will be evaluated for DLTs during the first cycle of treatment (28 days) [the DLT evaluation period]:

- If there are no DLTs in the first three participants in the DLT evaluation period, enrollment will be stopped.
- If one of the first three participants experiences a DLT in the DLT evaluation period, a Trial Steering Committee (TSC) will make the recommendation whether three additional participants will be enrolled to expand the number of participants to a total of six.
- If more than one of the first three treated participants experience a DLT, enrollment will be stopped.
- If the group is expanded and two or more of the six participants experience a DLT, enrollment will be stopped.

A DLT is defined as any adverse event or abnormal laboratory value assessed as unrelated to disease, disease progression, intercurrent illness or concomitant medications/therapies that satisfies at least one of the criteria listed in **Table 4**.

Table 4: Criteria for Defining Dose Limiting Toxicities

Toxicity		Any of the following criteria
Blood and lymphatic system disorders[a]		≥Grade 3 neutropenia (ANC <1.0 × 10 ⁹ /L) for >7 consecutive days
		≥Grade 3 thrombocytopenia (platelets <50 × 10 ⁹ /L) for >7 consecutive days
		Grade 4 thrombocytopenia
		Febrile neutropenia (ANC < 1.0 × 10 ⁹ /L with fever ≥38.5°C)
Investigations (renal)		≥Grade 3 serum creatinine
Investigations (hepatic)		≥Grade 3 blood bilirubin (> 3 × ULN)
		≥Grade 3 ALT or AST for > 7 consecutive days
		Grade 4 ALT or AST
		≥Grade 3 ALT or AST and ≥Grade 2 blood bilirubin
Investigations (metabolic)		Grade 3 lipase for >7 consecutive days
		Grade 4 lipase
Cardiac disorders		≥Grade 3
Gastrointestinal disorders		≥Grade 3 vomiting or nausea lasting more than 48 hours despite optimal antiemetic therapy[b]
		≥Grade 3 diarrhea lasting more than 48 hours despite optimal treatment
		≥Grade 3 pancreatitis
Skin and subcutaneous tissue disorders[c]: rash, photosensitivity or HFSR		Grade 3 rash/photosensitivity/HFSR for >7 consecutive days despite skin toxicity treatment (as per local practice)
		Grade 4 rash/photosensitivity/HFSR
General disorders and administration site conditions		Grade 3 fatigue/asthenia for >7 consecutive days
Ophthalmologic	Uveitis	Grade 3 for >21 consecutive days confirmed by ophthalmologic examination

Toxicity		Any of the following criteria
		Grade 4 confirmed by ophthalmologic examination
Any other eye disorders	Grade 3 for >21 consecutive days	
	Grade 4	
Other adverse events[d]		≥Grade 3 adverse events (excluding SCC)

Abbreviations: ALT = alanine aminotransferase; ANC = absolute neutrophil count; AST = aspartate aminotransferase; DLT = limiting dose toxicity; HFSR = hand-foot skin reaction (also known as palmar-plantar erythrodysesthesia [PPE] syndrome); NCI CTCAE = National Cancer Institute Common Terminology Criteria for Adverse Events; ULN = Upper limit of normal.

Grades according to NCI CTCAE grading system.

- [a] ≥Grade 3 anemia will not be considered a DLT unless judged to be a hemolytic process secondary to study treatment. ≥Grade 3 lymphopenia will not to be considered a DLT unless clinically significant.
- [b] Optimal therapy for vomiting or diarrhea will be based on study site guidelines with consideration of the prohibited medications listed in this protocol.
- [c] Squamous cell carcinoma reported to be an on-target side-effect that was manageable will not be considered a DLT.
- [d] An adverse event must be clinically significant to be defined as a DLT: alopecia, study treatment-related fever, electrolyte abnormalities (including K, NA, Cl, HCO₃, Mg, Ca, PO₄) that are ≤Grade 3 abnormalities will not be considered a DLT unless clinically significant.

To be evaluable for tolerability assessment by the TSC, participants must have *either* experienced an event meeting the DLT criteria during Cycle 1 *or* completed at least one cycle of study treatment and received at least 75% of the encorafenib dose intensity (administered dose in mg/planned dose in mg) in Cycle 1³.

Participants who terminate study participation for any reason other than an adverse event or abnormal laboratory value related to disease, disease progression, intercurrent illness or concomitant medications/therapies before having received at least the encorafenib dose intensity of 75% (administered dose in mg/planned dose in mg) in Cycle 1 will be considered ineligible for the safety assessment required for tolerability and will be replaced.

The TSC will analyse the available safety data and assess the toxicities as significant or not once the first three participants (and six participants if required) have fully completed the first cycle of treatment (28 days). The TSC will determine if encorafenib 300 mg QD is tolerable based on the DLT rate (DLTs observed in <33% of participants) and evaluation of the overall toxicity profile (based on deaths, treatment emergent SAEs, treatment emergent adverse events (TEAEs) leading to discontinuation and to dose interruption/reduction).

The TSC will make a recommendation if the dose of encorafenib 300 mg QD is not deemed tolerable.

³ Participants who require a dose interruption or reduction during Cycle 1 will remain evaluable for tolerability decisions if the reason for the reduction and/or interruption represents a DLT.

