Overall Design:	
This is a phase 1, multicenter, open-label, single-arm study to investigate the safety and tolerability of encorafenib 300 mg once daily (QD) monotherapy in adult Chinese participants with BRAF V600E mutant advanced solid tumors (unresectable metastatic melanoma or metastatic NSCLC), who are BRAF-inhibitor treatment-naïve and have failed the previous therapy(ies) for advanced metastatic disease or are not eligible to standard therapy. Participants will be eligible for the study based on identification of a BRAF V600E mutation in tumor tissue by a local National Medical Products Administration (NMPA) approved assay obtained prior to screening.
 
A dose limiting toxicity (DLT) is defined as any adverse event or abnormal laboratory value assessed as unrelated to disease, disease progression, intercurrent illness or concomitant medications/therapies resulting in the inability to tolerate at least 75% dose

	
intensity [(administered dose in mg/planned dose in mg) × 100] occurring within the first 28 days of study treatment (Cycle 1) that satisfies at least one of the predefined DLT criteria.
 
It is planned to enrol up to six evaluable participants using a 3+3 design. To be evaluable for tolerability assessment, participants must have either experienced an event meeting the DLT criteria in Cycle 1 or completed at least one cycle of study treatment and received at least 75% of the encorafenib dose intensity in Cycle 1. Non-evaluable participants, including withdrawals during Cycle 1 for reasons other than a DLT, will be replaced.
 
 • Three participants will initially be enrolled and receive encorafenib 300 mg QD, and will be evaluated for DLTs during the first cycle of treatment (28 days) [the DLT evaluation period]: 
 – If there are no DLTs in the first three participants in the DLT evaluation period, enrollment will be stopped. – If one of the first three participants experiences a DLT in the DLT evaluation period, a Trial Steering Committee (TSC) will make the recommendation whether three additional participants will be enrolled to expand the number of participants to a total of six. – If more than one of the first three treated participants experience a DLT, enrollment will be stopped. • If the group is expanded and two or more of the six participants experience a DLT, enrollment will be stopped.

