9.2. Sample Size Determination

The planned sample size is up to six evaluable participants based on a 3+3 design (see Section 4.1.1). No formal sample size calculation has therefore been performed and sample size is based upon empirical considerations.

Participants will receive encorafenib 300 mg QD. This dose will be considered acceptable if the observed Cycle 1 DLT rate in evaluable participants is <33% (e.g. less than one participant with DLTs out of three participants or less than two participants with DLTs out of six participants). To be evaluable, participants must have *either* experienced an event meeting the DLT criteria in Cycle 1 *or* completed at least one cycle of study treatment and received at least 75% of the encorafenib dose intensity (administered dose in mg/planned dose in mg) in Cycle 1 (see Section 4.1.1).

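### The stage 1 stopping rule counts DLTs in the first three treated participants, while replacement, the <33% rule and the primary analysis set count evaluable participants, so the literal count can understate toxicity

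*Protocol*

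**What the plan says.** Protocol 4.1.1 sets four enrolment rules, repeated in the synopsis (1.1) and SAP 1.2.

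- The stage 1 stop counts treated participants: "If more than one of the first three treated participants experience a DLT, enrollment will be stopped".
- The expansion rule counts participants without qualification: "If one of the first three participants experiences a DLT in the DLT evaluation period, a Trial Steering Committee (TSC) will make the recommendation" on whether to add three. The zero-DLT rule, which ends enrolment, is unqualified in the same way.
- So is the stage 2 stop: "If the group is expanded and two or more of the six participants experience a DLT, enrollment will be stopped".

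The surrounding text counts evaluable participants.

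- Size: "It is planned to enrol up to six evaluable participants using a 3+3 design". A participant is evaluable after a Cycle 1 DLT, or after completing a cycle with at least 75% dose intensity.
- Replacement, synopsis: "Non-evaluable participants, including withdrawals during Cycle 1 for reasons other than a DLT, will be replaced". Protocol 4.1.1 says that participants who leave before 75% dose intensity, with stated exceptions, "will be considered ineligible for the safety assessment required for tolerability and will be replaced".
- Acceptance, protocol 9.2 and SAP 3: "This dose will be considered acceptable if the observed Cycle 1 DLT rate in evaluable participants is <33" per cent, illustrated as "less than one participant with DLTs out of three participants or less than two participants with DLTs out of six participants".
- Primary analysis: the DDS, which consists of evaluable participants (protocol 9.3 and 9.4.2; SAP 4.2 and 5.3.2).

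The TSC criterion (synopsis, protocol 4.1.1 and 9.7, SAP 1.2 and 5.8.1) is a DLT rate below 33% of participants, without the word evaluable. SAP 1.2 schedules a TSC review after the DLT period of the first three participants, again without naming the base.

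**The concern.** A non-evaluable participant has had no DLT but still occupies one of the first three treated places. The replacement who takes over for the tolerability assessment is the fourth treated or later, so a DLT in that person falls outside the stage 1 count as written. The enrolment decision and the acceptance decision can then rest on different people.

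Two things are at stake. The plan can reach the branch that allows three more participants when two of three evaluable participants have already had a DLT. It can also end enrolment on a count of zero when the evaluable set holds one DLT, so the dose fails the acceptance rule and the second stage is never considered.

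**Working it through.** **1. The plan's own counts.** 0/3 = 0% and 1/6 = 16.7% are below 33%. 1/3 = 33.3% and 2/6 = 33.3% are not. This reproduces the counts in protocol 9.2.

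**2. Direction of the error.** Let D = DLT, N = non-evaluable and replaced, C = evaluable without DLT. Every D is evaluable, so the DLT count in the first three treated never exceeds the count in the first three evaluable.

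| Treated order | First 3 treated | First 3 evaluable | Branch on the literal text |
|---|---|---|---|
| D, C, N, then D | 1/3 | 2/3 (66.7%) | Expansion, if the TSC recommends it |
| C, C, N, then D | 0/3 | 1/3 (33.3%) | Enrolment ends; no second stage |

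With one N among the first three treated, six orderings behave like the first row: DNCD, DCND, NDCD, NCDD, CDND, CNDD.

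**3. Size of the expansion route** (treated count 1, evaluable count at least 2). Let p, n and c be the probabilities of D, N and C for each treated participant, and r = p/(p + c) the DLT probability given evaluable. The first three treated hold one D with either one N and one C, or two N:

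P = 6·p·n·c·r + 3·p·n²·[1 − (1 − r)²]

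The documents give neither rate, so both are assumptions.

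*Both rates per treated participant.*
- p = 0.30, n = 0.15, c = 0.55, r = 0.30/0.85 = 0.353: 6(0.30)(0.15)(0.55)(0.353) + 3(0.30)(0.0225)(0.581) = 0.0524 + 0.0118 = **6.4%**.
- p = 0.30, n = 0.30, c = 0.40, r = 0.30/0.70 = 0.429: 0.0926 + 0.0546 = **14.7%**.

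*Non-evaluability rate d applied only to participants without a DLT*, so n = (1 − p)d and c = (1 − p)(1 − d):

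| DLT rate p | d = 5% | 10% | 20% | 30% |
|---|---|---|---|---|
| 20% | 0.8% | 1.7% | 3.6% | 5.8% |
| 33% | 1.5% | 3.1% | 6.5% | 10.3% |
| 50% | 1.9% | 3.8% | 7.9% | 12.1% |

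The range of about 0.8% to 12% belongs to this second convention. It does not bound the first, as the 14.7% shows.

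**4. Size of the zero-count route** (treated count 0, evaluable count at least 1), at 30% and 15% per treated participant. This supposes that the replacement is enrolled although the zero-DLT rule ends enrolment. An evaluable count of zero implies a treated count of zero, so P = (1 − p)³ − (1 − r)³ = 0.343 − 0.271 = 7.2%.

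**5. No double counting.** P(at least 2 of 3) is 0.286 on evaluable and 0.216 on treated participants, a difference of 7.0%. Of this, 7.0% − 6.4% = about 0.6% has a treated count of zero. It leads to an enrolment stop and is already inside the 7.2%. The two routes are disjoint and total 6.4% + 7.2% = 13.6%.

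**The case against.** The strongest reply is that the enrolment rules implement a plan for up to six evaluable participants, and that in ordinary 3+3 use a replacement takes the vacated place. On that reading treated is loose wording and the counts agree. This is probably the intent, but the text does not say so, and the stop rule uses the word treated in all three places.

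A reader might infer more than the documents support, in four ways.

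- *That expansion is automatic.* It needs a TSC recommendation. The TSC's tolerability assessment is framed in evaluable participants and covers the overall toxicity profile, so it could decline. It also meets once three participants have fully completed Cycle 1, which an early withdrawal has not. The gap that remains is mainly a participant who finishes 28 days below 75% dose intensity, or a meeting held before the replacement finishes.
- *That this is the only toxicity stop.* The stage 2 rule is a second one: if the replacement counts among the six, two DLTs meet it at once. The sponsor may also end the study for serious emerging adverse events (protocol 10.1.2.1).
- *That an intolerable dose could be declared tolerable.* Under protocol 9.2 two DLTs give at best 2/6 = 33.3%, and the zero-count case gives 1/3 = 33.3%. Neither is below 33%. This protection comes from the word evaluable in 9.2 and SAP 3, which the TSC criterion lacks.
- *That 7.0% is the chance of wrongly reaching expansion.* That figure includes the 0.6% in which enrolment stops; the matching figure is 6.4%.

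Figure 1 is not visible in the text available, and the TSC Charter, which holds the operating procedures, is a separate document. Either may settle the base.

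**Conclusion.** The point holds as an inconsistency of counting base with a limited consequence. Read literally, stage 1 can treat 2/3 evaluable DLTs as 1/3, or 1/3 as 0/3, and the error runs only towards understating toxicity. The possible effects are exposure of up to three more participants, or a stop without the second stage.

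At the assumed 30% DLT and 15% non-evaluable rates per treated participant, the expansion route has probability 6.4%. This is an upper figure, because it makes no allowance for TSC discretion or the stage 2 stop. The contradiction itself does not depend on the assumed rates. It deserves correction because a pre-specified stopping rule should not rely on a committee to repair its count.

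**What to change.** Reconcile the passages on the base that the acceptance rule and the DDS already use:

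- In the synopsis, protocol 4.1.1 and SAP 1.2 (and Figure 1 if it carries the same wording), have all four enrolment rules refer to the first three, or the six, evaluable participants, with replacements included.
- Add evaluable to the TSC's <33% criterion in the synopsis, protocol 4.1.1 and 9.7, and SAP 1.2 and 5.8.1.
- State that the TSC's stage 1 decision waits until three participants are evaluable, unless two DLTs have already occurred. Align the SAP 1.2 meeting schedule and the TSC Charter with this.

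If every rule counts evaluable participants, the discordance is zero by construction. The cost is a wording change in the protocol and SAP, with a check of the Charter. It changes neither the planned number of evaluable participants nor the study procedures, though waiting for a replacement may delay the stage 1 decision.
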